#### 4.2.1 Initial Study Assessments

- Obtained prior to randomization
- Objective assessments to be obtained by providers blinded to study arm
  - o Penile length measured from pubic symphysis to glanular corona and penile tip
  - Penile curvature
    - Measured in A/P and lateral planes using a goniometer (per standard protocol)
    - Direction of curvature also assessed
    - Curvature document as uniplanar (i.e. 60 degrees dorsal, 30 degrees lateral) and composite (i.e. 90 degrees composite)
  - o Distance to curve measured from concave portion of curvature to corona of glans
  - o Indentations / hourglass deformities noted
  - Where possible (patients may decline), photographs obtained of the penis in the lateral and dorsal curvature after a pharmacologic erection has been obtained (per routine curvature assessment protocol). Images will be de-identified.
- Questionnaire on prior relevant disease history
- Subjective questionnaires
  - o IIEF-15
  - o PDO
  - Additional questions pre-treatment

#### 4.2.2 Subsequent Study Assessments

- Obtained at 3 and 6-month time points
- Objective assessments individual obtaining assessments will be blinded to study arm
  - o Penile length measured from pubic symphysis to glanular corona and penile tip
  - o Penile curvature
    - Measured in A/P and lateral planes using a goniometer (per standard protocol)
    - Direction of curvature also assessed

- O Distance to curve measured from concave portion of curvature to corona of glans
- o Indentations / hourglass deformities noted
- Photographs (if previously obtained and where possible) will be taken at the 3 and 6 month visits
- Subjective questionnaires (attached)
  - o IIEF-15
  - o PDQ
  - Additional questions (3 and 6-month form)

#### 4.2.3 Randomization and Blinding Protocol

Following enrollment and completion of the initial curvature assessment, patients will be categorized into one of six strata based on baseline variables (curvature 30-60 degrees, >60 degrees by dorsal primary, lateral primary, and ventral primary). Each strata will have a separate randomization table provided such that one of four possible outcomes will occur no less frequently than every four cases. This is done to better account for baseline variables that may impact outcomes and to assist with matching groupings appropriately.

The explanation of which grouping the patient is assigned will then be reviewed, and the patient will be provided with a RestoreX® device (if applicable).

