#### 4.1.2 Exclusion Criteria

- Prisoners
- Curvatures <30 degrees
- Stretched penile length <7 cm

- Currently undergoing intralesional injections for PD
- Erectile dysfunction (ED) unresponsive to phosphodiesterase-5 inhibitors or intracavernosal injection therapies
- Diabetes mellitus with evidence of end-organ damage (peripheral neuropathy, retinopathy, CKD stage III or higher, etc.)

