## 4.1.3 Setting

The current study will be conducted at the Mayo Clinic in Rochester, MN on Gonda 7 South (Dept of Urology). All patients will be recruited from [name] clinical practice, as [name] is the only Andrologist treating men with PD at Mayo Clinic Rochester. All aspects of recruitment, education, and objective assessments will occur within [name] practice.

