#### 4.1.4 Recruitment and Pre-Screening

Recruitment will occur from patients treated at Mayo Clinic for Peyronie's disease. Contact will occur via mailers and provider-initiated telephone calls after assuring that the patients meet the appropriate inclusion / exclusion criteria. Patients who would be interested in proceeding with the trial will be invited to an introductory meeting, at which time details of the study itself would be reviewed. No financial incentives will be provided to participate in the trial, however, participants would be given a RestoreX® device at no charge. Patients will not be charged for any visits related to the study, and no labs or other testing will be obtained which require payment.

Patients indicating that they would wish to participate will be reviewed to again assure that they meet the appropriate inclusion and exclusion criteria.

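### Read as fixed blocks of four, the allocation rule makes the last place in each block foreseeable: at most 26–30 of 120 assignments, fewer in practice

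*Combined protocol and SAP*

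**What the plan says.** Section 4.2.3 forms six strata (two curvature bands by three primary directions), gives each its own table, and requires that "one of four possible outcomes will occur no less frequently than every four cases". One stated purpose is "to assist with matching groupings appropriately". The section does not use the word block, and does not say whether a block size varies, who holds the tables, or how the next assignment is hidden.

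The order of events is clear. Section 4.2 puts consent before randomisation, Section 4.2.1 puts the baseline assessments before it, and Section 4.2.3 says: "Following enrollment and completion of the initial curvature assessment, patients will be categorized into one of six strata". Then "The explanation of which grouping the patient is assigned will then be reviewed", and a device is handed over only if the arm calls for one. The assignment is therefore open to the patient and to whoever explains it. Sections 4.2.1 and 4.2.2 blind the objective assessors to arm.

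On recruitment, Section 4.1.4 states "Recruitment will occur from patients treated at Mayo Clinic for" Peyronie's disease, with contact made "after assuring that the patients meet the appropriate inclusion / exclusion criteria". One of those criteria is the exclusion "Curvatures <30 degrees" (Section 4.1.2). Section 4.1.3 adds: "All aspects of recruitment, education, and objective assessments will occur within" a single practice. Section 4.1.5 aims for 25 men per arm and expects to enrol about 120.

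**The concern.** In an open-label trial, a fixed block size equal to the number of arms lets the last assignment of each block be worked out from the earlier ones. Blinded outcome assessment does not prevent this, because it protects measurement and not the next assignment.

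The possible route to harm is narrow. The men are already patients of the practice and are checked against criteria that include curvature before contact. A recruiter might therefore anticipate a man's stratum before consent and, even unintentionally, vary encouragement or the timing of entry. That the records show both degree and direction of curvature is an inference; the protocol does not say so.

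The comparison of traction with no traction (Section 4.3.3) would be the most exposed. The planned ANCOVA adjusts for curvature direction, curvature degree and baseline length, so it would not correct an imbalance in motivation or disease stability. The investigator is also the device's inventor (Section 6.1), so a predictable list invites criticism that is easy to avoid.

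**Working it through.** **Inputs.** Four arms, three with a device and one control (Section 4.2); six strata with separate tables (4.2.3); 120 enrolled and 4 × 25 = 100 as the target (4.1.5); f = 0.3370 at 80% power and 0.05 significance (4.3.2). Assumed reading: blocks of four, one place per arm.

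**The plan's own figure.** The plan gives no figure for predictability. Its effect size is needed only to price the fix. A noncentral F calculation with 4 groups and N = 100 gives f = 0.33699 at 80% power, which agrees.

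**Upper bound on certain assignments.** One assignment is certain per completed block, so the count is Σ floor(n_s/4) = (N − Σ r_s)/4, where each remainder r_s is 0 to 3. Six remainders sum to at most 18, and the sum must be a multiple of 4 for N = 120 or 100, so it lies between 0 and 16.

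- N = 120: (120 − 16)/4 = 26 to 120/4 = 30.
- N = 100: (100 − 16)/4 = 21 to 100/4 = 25.

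This holds for any split over the strata. The simulated mean for 120 is about 27.8 (27.8/120 = 23%). A quarter of these are control: 27.8/4 ≈ 7.

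**Guessing device or control.** Always guessing device is right 75% of the time. With a tally, accuracy by place in the block is 75%, 75%, 75% and 100%, so the mean is 81.25%, a gain of 6.25 points. For the exact arm it is (1/4 + 1/3 + 1/2 + 1)/4 = 52.1%, against 25%. Incomplete blocks lower both slightly (table).

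**Fixed fours against a 4/8 mix.** Simulation with 1,500 runs per setting. Stratum shares were equal or 40/20/15/10/10/5%. The observer knows the block rule (4 and 8 equally likely in the mix) and all past assignments in the stratum. Power takes control as differing from three equal device arms.

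| | Fixed 4, N=120 | Mix, N=120 | Fixed 4, N=100 | Mix, N=100 |
|---|---|---|---|---|
| Exact arm certain | 27.7–27.8 | 7.3 | 22.7 | 5.7 |
| Control certain | 6.9 | 1.8 | 5.7 | 1.4 |
| Device or control certain | 50.1 | 16.1–16.2 | 41.1–41.2 | 12.9–13.1 |
| Device-versus-control guess right | 80.8% | 79.0% | 80.6% | 78.9–79.0% |
| Exact-arm guess right | 50.6% | 46.8% | 50.2–50.3% | 46.4% |
| SD of an arm's size | 0.97–0.99 | 1.19–1.20 | 0.97–0.98 | 1.18–1.19 |
| ANOVA power at f = 0.337 | 87.5% | 87.5% | 79.9% | 79.9–80.0% |

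**Sparse strata under the mix.** An arm can be absent only if the first block has size 8 (probability 1/2) and both of that arm's places fall among those not yet used.

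- 6 men: 1/2 × 4/28 = 7.1%.
- 5 men: 1/2 × 24/56 = 21.4%.
- 4 men: 1/2 × 54/70 = 38.6%.
- 7 or more men: 0.

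Under fixed fours the figure is 0 from 4 men upward.

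**Usable share.** The documents do not say for how many men the stratum could be foreseen before consent. Taking that share as an assumption, the certain assignments for 120 men under fixed fours are 27.8 × 0.25 ≈ 7, 27.8 × 0.5 ≈ 14, or 27.8 × 1 ≈ 28. The corresponding controls are about 2, 3 and 7.

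**The case against.** The strongest reply is that 26–30 is a ceiling. Reaching it needs the fixed-block reading, a tally of all six strata, and knowledge of a man's stratum before he consents. Once he has consented and been measured, foreseeing his arm cannot change whether he enrols. Pre-screening needs only the 30-degree cutoff, not the 60-degree split or the primary direction that define the strata. Men on other treatments are asked to stop them for at least 4 weeks before the appointment, so older measurements may not settle the band. Rescheduling in Section 4.2 is the patient's choice and gives recruiters no stated control over order of entry. All of this stands, and it is why the count is given as an upper bound.

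It is also fair that safety is primary, the efficacy comparisons are secondary and objective assessors are blinded. The fix barely changes guessing, and a concealed list does not stop a tally of assignments already disclosed. That limits the benefit. It does not remove it, because the mix eliminates most of the certainty and the concealed list rules out reading ahead.

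A reader might infer more than the text supports:

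- That recruiters see the tables. The protocol does not say who holds them, which is missing detail and not evidence of access.
- That every run of four consecutive cases must contain each arm. The list would then be a repeating cycle, with 120 − 6 × 3 = 102 assignments foreseeable. The sentence does not require this, and the milder block reading is the natural one.

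**Conclusion.** The point holds as a modest design weakness. On the natural reading of Section 4.2.3, the last assignment of each completed block is certain to anyone tracking that stratum. The upper bound is 26–30 of 120 assignments (21–25 of 100), with about 7 of the 120 known to be control. The gain in guessing device against control is about 6 points.

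This rests on three assumptions: fixed blocks of four, a full tally over six strata, and foreknowledge of each man's stratum. The planned order of consent, baseline, stratum and randomisation makes the usable number smaller, by an amount the documents do not allow one to fix. It would be tempting to conclude that a quarter of the allocations were open to manipulation, or that the comparisons are biased. The documents support neither: they show no one keeping a tally and no selective entry. The change is worth considering because it is cheap, not because the results are shown to be at risk.

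**What to change.** Replace the every-four-cases sentence in Section 4.2.3 with text to this effect: *Within each of the six strata, men are allocated equally to the four groups by permuted blocks of randomly varying size. The sizes are kept in a separate document withheld from recruiting and assessing staff. Each assignment is released from a concealed list, sealed or electronic, only after consent, baseline measurements and stratum are recorded as final.* Sizes 4 and 8 are one suitable choice for the separate document. The sequence of consent, baseline and randomisation is already planned; the varying sizes, the final record and the concealed list are new. If enrolment has begun, apply the change to the remaining assignments.

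The cost is a short amendment and new tables. Balance, which the existing rule was meant to serve, loosens a little: the SD of an arm's size rises from about 1.0 to about 1.2, and an arm may be absent from a stratum of six or fewer men at the rates worked out above. That matters only if some strata prove very sparse. Power at the plan's effect size is essentially unchanged. The team should not expect the mix to make allocation unguessable, since its benefit lies in removing most of the certainty.

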## 4.2.4 Assessment of Curvature and Length

To assure blinding of outcomes, where possible, men will have photographs obtained of the penis in the lateral and dorsal curvature after a pharmacologic erection has been obtained (per routine curvature assessment protocol). Images will be de-identified, and curvatures will be assessed in two planes (lateral and dorsal).

Penile length measurements will be obtained by two individuals using a standardized ruler prior to beginning the pharmacologic erection. Where possible, the same individuals will perform the measures at each visit.

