## 3.2 Preliminary Data

Currently, there is a small amount of preliminary data available on the RestoreX® instrument. During the developmental phase of the device, a quality improvement project was performed to evaluate the clamping portion (see **Attachment – Quality Improvement Summary**). It was felt that the clamp represented the most critical aspect of the device, as this was where the majority of discomfort occurred with other devices. Additionally, the clamp needed to provide sufficient friction to allow adequate traction without having the glans of the penis dislodge from the device.

A total of 15 patients participated in the quality improvement project and had the clamps applied under direct supervision for 30 minutes. After the 30 minutes, all patients reported 0/10 pain, and only minimal transient erythema was documented by the physician. The clamp was again applied, and traction forces were administered to determine if the clamp was able to remain intact despite stretching forces applied. This also resulted in a successful outcome, with all patients able to successfully achieve a minimum required tension of 1 kg, with a 36% safety factor achieved before any discomfort was reported among any patient. During the testing, patients reported improved comfort with the use of a wrap such as gauze or Coban, which permitted additional traction in all patients.

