## 4.2 Study Schema

Once patients have agreed to receive further information on the study, an initial consult will be established. Patients who are currently taking other therapies for PD will be requested to stop these therapies for a minimum of 4 weeks prior to the appointment to assure an adequate washout period prior to being enrolled.

During the initial appointment, the patient will receive a description of the study, initial education on how to use the device properly, and informed consent. Those consenting to the procedure will

receive initial study assessments (see below). Those wishing additional time to consider enrollment may be rescheduled to a later date if desired. Once consent is completed, the patients will be randomized into one of four groups: PTT 30 min 1x/day, 30 min 2x/day, 30 min 3x/day, or control (no treatment).

Patients will then begin using the devices as previously instructed for the times appropriate to their group. After 3 months (+1.5 months permitted), patients will return for subsequent assessments (see below). After completion of the subsequent assessments, patients will begin a 3-month, open-label phase of the trial. During this period, the patients will be allowed to use the device for 30 minutes at a time, with a frequency to be determined by the patient.

After completion of the open-phase portion of the trial, patients will undergo final assessments, which are identical to the 3-month assessments. Patients will then be encouraged to self-report any additional adverse events (AE's) that they encounter over the subsequent 3 months after discontinuing the therapy and will be contacted by telephone for a final question / adverse event assessment (9 months after study initiation).

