## 4.3.2 Power Analysis

This is the first study which will be performed for this specific device. As such, the objectives are to assess safety with various dosing protocols. Regarding our secondary end points of penile length and curvature improvement, prior studies evaluating the role of PTT in the early phase of PD have

demonstrated significant improvements with study sizes of 96 patients, which is consistent with the current study schema.[17]

A power analysis was also performed using ANOVA with anticipated sizing of 25 individuals into 4 arms. This provides an effect level of 0.3370 using 80% power, with 0.05 significance established for curvature assessment. Therefore, the study is likely powered to demonstrate large changes in curvature but may not be adequately powered to identify small or medium differences in curvature between groupings. The study is adequately powered to detect reasonable changes in penile length.

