#### 4.3.3 Statistical Analysis

All data will be entered into JMP Pro 10.0.0 (SAS Institute, Cary, NC). Differences between groupings will be analyzed using tests appropriate to the specific conditions: Wilcoxon, matchedpairs, student's t-test, ANOVA, ANCOVA, chi-squared, or Fisher's tests. All relevant tests will be 2-sided, with a p-value of <0.05 defined as significant. Differences in AE's will be determined based on total number of reported events as well as individual assessments of each individual event.

During the first phase of the study, results will be analyzed as a whole to determine the percentage of men who were non-compliant (both in methods of utilizing the device and percentage of time spent using the device) or dropped out. These data will determine the ability of men to utilize the device as recommended. Data will be analyzed both with and without these non-compliant / dropout men included. Non-compliance will be determined by failure to bury the white indicator line regularly with straight stretch, failure to achieve 90 degree bending during majority of uses, and failure to perform traction for at least 90% of days recommended.

Analyses will be performed using comparisons within patients (changes from baseline to 3 months, from 3 months to 6 months, from baseline to 6 months) and between groupings. ANCOVA will be used (adjusting for baseline values of curvature direction, curvature degree, and baseline penile length). Additional analyses will be performed to analyze the impact of prior treatments (such as intralesional injections) on outcomes. The use of ANCOVA is anticipated to increase the effect size slightly to 0.302 (assuming R^2 value of 0.2 for curvature direction, curvature degree, and baseline penile length).

Assessments will also be performed comparing any degree of traction (i.e. groups 2-4) against no traction. Additional assessment will also be performed based on the total duration of traction applied (time per day multiplied by number of days used) to assess for differences in outcome variables.

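### No interval is set between the last device session and the month-3 measurements, so any short-lived effect of recent use is confounded with arm, and clamp marks could reveal device use to the assessor

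*Combined protocol and SAP*

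**What the plan says.** Section 4.2 randomises men to 30 minutes of traction once, twice or three times daily, or to no treatment. It continues: "Patients will then begin using the devices as previously instructed for the times appropriate to their group". They return at 3 months (up to 1.5 months later is allowed), and open-label use starts only once those assessments are done. No pause before the visit is described. The only washout in the protocol is at least 4 weeks off other Peyronie's therapies before the initial appointment.

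On measurement, section 4.2.4 states: "Penile length measurements will be obtained by two individuals using a standardized ruler prior to beginning the pharmacologic erection". Curvature is assessed under pharmacologic erection, with de-identified photographs where they can be obtained. For the objective assessments at 3 and 6 months, section 4.2.2 requires: "individual obtaining assessments will be blinded to study arm".

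Section 3.2 reports on 15 men who wore the clamp for 30 minutes under supervision: "only minimal transient erythema was documented by the physician". The month-9 contact is by telephone, so it yields no physical measurement.

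**The concern.** The treatment rationale in section 3 is lasting tissue remodelling. A reading taken soon after a stretch would also include any short-lived elongation, straightening or swelling. If visits are not timed, the chance of a recent session depends on assignment: none in control and, in the device arms, higher with more daily sessions. Because assignment itself causes the difference, randomisation does not balance it. The planned ANCOVA adjusts only for baseline curvature direction, curvature degree and length, so it does not remove it either. The artefact would point the same way as a real benefit in the between-group comparison, the any-traction-versus-none comparison and the total-duration analysis of section 4.3.3.

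The second route is blinding. A mark left by the clamp could tell the assessor that the man has a device. Length is the more exposed outcome, because it is read directly by ruler with no photographic record to fall back on.

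**Working it through.** **Inputs from the documents**
- Sessions per day: 0, 1, 2 or 3 (section 4.2).
- Size: "A power analysis was also performed using ANOVA with anticipated sizing of 25 individuals into 4 arms" (section 4.3.2), so N = 100.
- Level: "All relevant tests will be 2-sided, with a p-value of <0.05 defined as significant" (section 4.3.3).
- Detectable effect: "This provides an effect level of 0.3370 using 80% power, with 0.05 significance established for curvature assessment" (section 4.3.2).
- With covariates: "The use of ANCOVA is anticipated to increase the effect size slightly to 0.302", at R² = 0.2 (section 4.3.3).

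**Assumed, because the documents give no value**
- A 16-hour day with sessions at random times.
- A carry-over window of 2 or 4 hours.
- A mean transient shift of b SD in the 3x arm. No SD for length is given, so SD units are the only usable scale.

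**Step 1: the plan's own figures.** One-way ANOVA, 3 and 96 degrees of freedom, noncentrality N·f². Solving for 80% power gives f = 0.33699, which matches 0.3370. For ANCOVA, 0.337 × √(1 − 0.2) = 0.3014, or 0.3016 with three covariates taken off the error degrees of freedom. This matches 0.302 to rounding.

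**Step 2: chance of recent use at an untimed visit.** For n sessions a day and a window of h hours, P = 1 − (1 − h/16)^n.

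| Window | Control | 1x | 2x | 3x |
|---|---|---|---|---|
| 2 h | 0 | 12.5% | 23.4% | 33.0% |
| 4 h | 0 | 25.0% | 43.8% | 57.8% |

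**Step 3: false-positive rate with no lasting effect.** Let the mean shifts be 0, b/3, 2b/3 and b. This is close to the 2-hour row, where 1x and 2x stand at 0.38 and 0.71 of 3x. Then f = b·√(5/36) = 0.3727b and noncentrality = 100·f² = 13.89b². The any-traction contrast compares 75 men with 25 at a mean difference of 2b/3.

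| b (SD) | f | Noncentrality | Four-arm ANOVA | Any traction vs none | ANOVA, three device arms only |
|---|---|---|---|---|---|
| 0.1 | 0.037 | 0.14 | 5.8% | 5.9% | 5.4% |
| 0.25 | 0.093 | 0.87 | 10.4% | 11.0% | 7.6% |
| 0.5 | 0.186 | 3.47 | 30.3% | 29.8% | 16.3% |

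**Step 4: what those shifts would require.** The arm's mean shift is roughly the chance of recent use times the transient effect in a recently treated man. With the 2-hour window, b = 0.1, 0.25 and 0.5 need individual effects of 0.1/0.330 = 0.30, 0.25/0.330 = 0.76 and 0.5/0.330 = 1.52 SD. With the 4-hour window they need 0.1/0.578 = 0.17, 0.25/0.578 = 0.43 and 0.5/0.578 = 0.87 SD.

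**Step 5: if every device user has a session just before the visit.** The shifts become 0, b, b, b, with no gradient among device arms. For b = 0.1, 0.25 and 0.5 the four-arm ANOVA rejects in 6.1%, 12.5% and 40.0% of trials, and any traction versus none in 7.1%, 18.8% and 57.3%.

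**The case against.** The strongest reply is that the mechanism is conjectural. The documents report no transient lengthening or straightening, no duration for either, and no erythema by frequency of use. What they do report is minimal redness after one supervised application. A reader might infer that a spurious dose response is established; it is not. Only the unequal chance of recent use follows from the design, and even that requires untimed visits. At 0.1 SD the ANOVA error rate barely moves. This part of the objection stands and limits the point to an uncontrolled risk of unknown size.

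Four further limits also stand:
- **Month 6.** A reader might take men to be on the device at every measurement. Open-label frequency is chosen by the patient, and the final assessments follow completion of that phase. Whether men are still using the device then is not stated, so the assigned-frequency argument belongs to month 3.
- **Blinding.** A reader might conclude that the assessor would see dose. Erythema can suggest device rather than control, but not 1x rather than 3x, and no rate is available to say how often it would be seen.
- **Curvature.** De-identified photographs partly protect it against assessor bias, though only where obtained. They do not remove a physical carry-over effect.
- **Unseen attachments.** The visit forms and the routine curvature protocol are not available, and the duration analysis needs usage data. Last-session time may be captured there, but the protocol text neither requires it nor uses it.

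Length and curvature are also secondary; the primary objective is safety. That limits the weight of the point without answering it. The plan allows for carry-over from other therapies at baseline but makes no matching provision for its own device at the outcome visit.

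**Conclusion.** The point holds for month 3. The protocol lets recency of use differ systematically by arm, and neither its randomisation nor its covariate adjustment corrects for that. A lasting change therefore cannot be separated from a transient one at that visit. Under the assumptions shown, the four-arm false-positive rate lies between 5.8% and 30.3% for shifts of 0.1 to 0.5 SD in the 3x arm. The documents do not say where in that range, or outside it, the truth lies, and the upper end with a 2-hour window needs a large individual effect (about 1.5 SD). Possible unblinding is a smaller, device-versus-control concern, chiefly for length. The point bears on how the secondary efficacy results are read; it does not touch the safety objective or the power calculation, which reproduces. The change is worth making because timing that is not recorded during the trial cannot be reliably recovered afterwards.

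**What to change.** In sections 4.2.2 and 4.2.4:
1. Take length and curvature before any device session that day, in all arms, with a minimum interval since the last session chosen by the sponsor. The same-day rule alone is not enough: a man who last used the device the previous evening and one who last used it the previous morning would still differ.
2. State the rule in the visit reminder.
3. Record the date and time of the last session on a form the assessors do not see.

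In section 4.3.3:
1. Report the interval by arm, with a sensitivity analysis excluding men measured soon after a session. Fix the cut-off before the data are seen.
2. State that month-3 results are on-treatment values and do not show persistence after stopping.

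The cost is one visit instruction, one form field and one table. Visit times become less flexible, and reported gains may be slightly smaller. Sample size and power are unchanged (f = 0.337 with 25 per arm).
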